### 3. Background

Linkage to HCV care among people co-infected with HIV/HCV is poor. The greatest gap in the United States HCV care cascade begins between diagnosis and linkage to care. Only 25% of PLWH with chronic HCV have attended an HCV appointment, and less than half of those have ever initiated HCV treatment. A large cohort study in Baltimore found that only 21% of injection drug users with HCV had ever seen an HCV specialist. At the Johns Hopkins Moore Clinic, less than half of patients who are referred to an HCV specialist by their primary care provider actually attend the scheduled specialty appointment.

The perceived threat of HCV and perceived need for HCV care among patients is low. This perception, coupled with the fact that HCV is a “silent epidemic”, places PLWH at great risk. Qualitative studies describe that the absence of HCV-related symptoms leads to little interest in receiving HCV treatment. This is exacerbated by a lack of knowledge about HCV and available therapies; horror stories about interferon-related side effects and old ineffective treatments dominate conversations among peers with HCV despite these barriers being minimized with new all-oral therapy. People with HCV also report low motivation to engage in HCV care due to competing demands from work, school or caregiving responsibilities. Therefore, interventions to increase HCV knowledge and motivation, such as education, patient navigation, and appointment reminders are needed to improve linkage to HCV care.

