## 7. Study Statistics

### Analysis:

Data will be cleaned and efforts made to minimize the effects of missing data. All provider visits at Johns Hopkins are registered in the electronic medical record, so absence of a registered appointment during the study period will be considered non-attendance for the primary outcome variable. A computer-based data collection method will be used for data collection of independent variables in attempt to minimize missing data. Exploratory and descriptive analysis will be completed for all study variables. Variables will be tested for normality and examined with means and standard deviations or medians and interquartile ranges accordingly. Baseline characteristics comparing the two groups (usual care vs. intervention) will be assessed. Any differences between the groups will be adjusted for in further analysis. The significance level will be set at 0.05. All tests will be two-tailed and analyzed by intention-to-treat.

**Primary Outcome:** The primary outcome is linkage to care, measured by attendance at the Viral Hepatitis Center (either traditional care or an HCV-treating clinical trial) within 60 days of randomization (yes/no). This hypothesis will be tested using a two-sample z-test for the difference in independent proportions comparing the intervention to usual care groups.

**Secondary Outcome:** The secondary outcome is time to HCV treatment initiation, measured by the number of days from randomization to the date HCV treatment is initiated according to the medical record. Kaplan Meier estimates will be conducted to compare time to HCV treatment initiation between participants in the intervention group and the usual care group, and a log-rank test will be used to test the difference. Covariates (age, sex, race/ethnicity, HCV knowledge, substance use, fibrosis score, CD4+ T cell count, HIV viral load, care giving responsibilities, and participation in Cure Club) will be included in the Cox regression model. To account for a time to treatment initiation greater than the observed time period of 6 months, right censoring will be implemented for participants who have not initiated HCV treatment at the end of the 6-month period.

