### **Sample Size Justification:**

Currently, 40% of new Viral Hepatitis Clinic appointments are attended by patients. Based on prior studies testing the intervention components in similar populations, including persons living with HIV and/or substance use disorders, it is expected that the intervention will improve the primary outcome of linkage to care by 18-30%. Although the effect size is not known in the context of HCV, we estimate an improvement in linkage of 20% (i.e., 60% attendance [0.60] in the NCM group compared to 40% attendance [0.40] in the usual care group) based on these prior studies. Using these figures and a two-tailed test with an alpha of 0.05, a conservative estimate of the total sample size required to achieve 80% power is 97 per group, or a total of 194 participants (G\*Power 3.1.9.2). With a sample size of 100 participants in each group, there should be an adequate number of participants to detect a difference in proportion of linkage to care for the primary aim.

For Phase 2, participants with successful linkage to clinical care from Phase 1 (those who attend  $\geq 1$  appointment at the Viral Hepatitis Clinic within 60 days) will be included. Therefore, the eligible sample size will be less than 40-60% of the original sample size because a linkage to care proportion of 0.40-0.60 is expected, and some participants will link to a clinical trial and not be included in this outcome. This is a secondary outcome and estimated effect size is unknown. However, with 100 participants in this group (half of the total sample size), we will have 90% power to detect a hazard ratio of 2.

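### The adjusted Cox model for time to HCV treatment has at least 11 parameters for a probably small, unstated number of events; moderate overfitting is likely, and a short fixed covariate set would largely avoid it

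*Combined protocol and SAP*

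**What the plan says.** All references are to the combined protocol and SAP.

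- **Section 7, Secondary Outcome.** Time from randomisation to treatment start is compared by Kaplan-Meier, and "a log-rank test will be used to test the difference". A Cox model follows, with these terms: "Covariates (age, sex, race/ethnicity, HCV knowledge, substance use, fibrosis score, CD4+ T cell count, HIV viral load, care giving responsibilities" and Cure Club participation. Participants not treated by 6 months are censored.
- **Section 7, Analysis.** A general rule can add terms: "Any differences between the groups will be adjusted for in further analysis". On testing, "The significance level will be set at 0.05" and "All tests will be two-tailed and analyzed by intention-to-treat".
- **Section 7, Exploratory Analysis.** A correlation screen for dropping covariates is described, but only for the logistic model of linkage. The Cox model has no reduction rule and no penalisation.
- **Section 7, Sample Size Justification.** The Phase 2 set is those who link to clinical care, put at below 40-60% of the original sample because some will link to a clinical trial instead. The power statement is made "with 100 participants in this group (half of the total sample size"), for a hazard ratio of 2 and 90% power. Neither an event count nor a six-month initiation rate is given.

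**The concern.** What limits the size of a Cox model is the number of events, and here that is the number of participants who start HCV treatment within 6 months. With few events per parameter, maximum partial likelihood tends to push a real effect away from 1, and the model-based standard error tends to be too small.

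The log-rank test yields a p-value and Kaplan-Meier yields curves. The adjusted hazard ratio is therefore the only hazard ratio that the plan would produce for Aim 2, and the one readers are likely to quote. One listed term, Cure Club participation, can also follow from allocation, because referral to that group may be part of the Phase 1 plan. That is a further reason to look at the list.

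**Working it through.** **1. The plan's own power figure.** With 1:1 allocation, two-sided alpha 0.05, HR 2 and 90% power:
- Schoenfeld: d = 4(1.960 + 1.282)² / (ln 2)² = 4 × 10.51 / 0.480 ≈ 88 events.
- Freedman: d = (1.960 + 1.282)² × (2 + 1)² / (2 − 1)² = 10.51 × 9 ≈ 95 events.
- If all 100 participants had an event, power would be 93.4% (Schoenfeld) or 91.5% (Freedman).

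The stated 90% is reproduced only if about 88-95 of the 100 start treatment within 6 months.

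**2. Parameters.** Ten covariates + arm = 11. If race/ethnicity, substance use and fibrosis score take two terms each (an assumption, as no coding is given), 11 + 3 = 14.

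**3. Participants.** 40-60% of 200 = 80-120, and the plan expects fewer.

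**4. Events (assumed).** The Abstract gives about 7% treated. Section 3 gives 25% having attended an HCV appointment, and says that "less than half of those have ever initiated HCV treatment".
- Lower figure: 7% / 25% = 28%, or 28 of 100.
- Upper figure: under 50%, or fewer than 50 of 100.

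These are historical figures for ever starting treatment, not six-month rates in this clinic.

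**5. Events per parameter.**
- 28 events: 28/11 = 2.5; 28/14 = 2.0.
- 50 events: 50/11 = 4.5; 50/14 = 3.6.
- 88 events: 88/11 = 8.0.

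**6. Simulation.** There were 3,000 trials per setting, with exponential times, administrative censoring set to reach the target events, and independent covariates (five binary). Ten covariates had log hazard ratios of 0.2-0.4 in absolute size; the 15-parameter model adds four null covariates. The arm-only rows are a benchmark generated without covariate effects. Coverage is of the usual Wald 95% interval for arm.

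| Model | n | Events | Median HR (true 2) | Model SE / true SD | Coverage (true HR 2) | Type I error (true HR 1) |
|---|---|---|---|---|---|---|
| Arm only | 100 | about 28 | 1.98 | 0.97 | 95.6% | 4.1% |
| Arm only | 100 | about 50 | 2.00 | 0.97 | 94.6% | 5.1% |
| 11 parameters | 100 | about 28 | 2.15 | 0.91 | 93.4% | 7.8% |
| 11 parameters | 100 | about 50 | 2.20 | 0.92 | 92.9% | 7.3% |
| 15 parameters | 100 | about 28 | 2.26 | 0.84 | 91.2% | 7.3% |
| 15 parameters | 100 | about 50 | 2.18 | 0.88 | 91.2% | 8.0% |
| 11 parameters | 200 | about 28 | 2.08 | 0.92 | 94.8% | 5.6% |
| 11 parameters | 200 | about 50 | 2.07 | 0.92 | 93.6% | 6.3% |

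The Monte Carlo standard error of a 5% rate is √(0.05 × 0.95 / 3000) = 0.4 percentage points. At a true HR of 1, the median estimate in the adjusted models is 0.98-1.02.

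Further simulations with other covariate effects and 11-14 parameters agree. At n=100 and 28-50 events they give a median HR of about 2.1-2.3 and coverage of 90-94%. Arm plus three covariates gives 1.92-2.06 and 94-96%. At the 88 events that the power statement implies, coverage with the long model is still 91-93%.

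**The case against.** **The event range is not the plan's.** This stands. The 28-50 figure joins percentages from two sections. The Abstract pairs its 7% with less than half linked, which gives only a floor of 7/50 = 14%. The Abstract also describes care at a turning point, so historical rates may be too low. The power statement implies 88-95 events, or about 8 per parameter with 11 parameters. However, the plan never states that count, and 88 of 100 treated within 6 months sits badly with its own account. It describes a Metavir threshold for treatment in Maryland, possible ART modification, a viral load recheck 4-8 weeks later, and reimbursement delays. Some under-coverage remains even at 88 events.

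**The hypothesis does not rest on this model.** This also stands. The log-rank test is unadjusted, so overfitting does not touch it.

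**The distortion is modest.** This stands too. The shift from 2 to about 2.2 is small beside the sampling error at these event counts, and it is smaller with all 200 analysed.

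**A reader might infer** that the adjusted hazard ratio is bound to be inflated and its interval clearly wrong. The documents do not support that. There is no shift at a true HR of 1, some settings are close to nominal, and the plan does not specify an interval method. More alarming results can be produced: n=60 with 22 events and 14 parameters gave a median HR of 2.58 and 88% coverage in one simulation. Those events lie below the assumed range.

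**Conclusion.** The concern holds in moderate form, as a cheap improvement. The Cox model is large for the number of events it is likely to have, and the plan gives neither an event count nor a rule for reducing it. At n=100 and an assumed 28-50 events, a true hazard ratio of 2 would be estimated at about 2.1-2.3, with coverage of about 90-95% and type I error of about 5-9%.

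These sizes rest on the assumed events, the coding of the covariates, independent covariates of modest effect, and Wald intervals. Correlated or sparse covariates would make matters worse; an analysis of all 200 would make them milder. It would go too far to conclude that the Aim 2 test is invalid.

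A separate matter follows from the same figures: with 28-50 events, Schoenfeld power at HR 2 is 45-69%, not 90%. Shortening the covariate list does not address that.

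**What to change.** In section 7, Secondary Outcome:

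1. Limit the adjusted Cox model to arm plus three or four named covariates from the existing list, each measured before randomisation and entered as one parameter. Cure Club participation would not qualify unless it is recorded before randomisation.
2. State that this model is exempt from the general rule on adjusting for baseline differences. Otherwise the dropped covariates can return.
3. Leave the full list to the descriptive Aim 3 model.
4. If all ten must stay, use Firth penalisation with profile-likelihood intervals and label the model supportive. In simulation, Firth with Wald intervals restored coverage only in part; the profile-likelihood version was not simulated here.

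The cost is a change of wording. The downside is that chance imbalance in the dropped covariates goes unadjusted in this model. The choice of three or four is a judgement; arm plus three covariates is what the simulations support.

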HIV-HCV drug interactions will exist for up to 88% of PLWH. HCV treatment guidelines no longer separate patients with HIV/HCV co-infection from those with HCV only because cure rates are similar in both groups (over 90%). Currently, the only difference in management of HCV in PLWH is the need to manage drug interactions. Patel and colleagues (2015) conducted a cross-sectional study to determine the frequency of contraindicated drug-drug interactions when PLWH are prescribed HCV therapy. Examination of medication lists revealed that the prevalence of interactions was as high as 88.4% depending on the HIV and HCV regimens. Based on these results, it is likely that a large proportion of PLWH who are initiating HCV treatment will have to modify their HIV treatment regimen. Modifying HIV treatment regimens can take months and deter PLWH from starting HCV treatment. A prior study found that HIV combination antiretroviral therapy (ART) modifications can negatively impact quality of life and increase HIV symptom burden. Therefore, new approaches to modifying ART that minimize barriers to HCV treatment initiation are urgently needed to smooth the transition for PLWH.

Interventions that increase perceived need and maximize enabling resources have the potential to improve the HCV care cascade for PLWH. Nurse case management (NCM) components used in similar contexts can be combined to achieve this improvement. Even in the era of interferon, brief HCV education alone significantly increased knowledge and linkage to HCV care by 14-25%. Adding strengths-based NCM and care coordination improves linkage to HIV or HCV care by up to 30%. Reminder systems using text and phone messages are also effective strategies to increase linkage to HIV care and substance use services in combination with other interventions. Finally, the addition of care coordination for ART modification will further participants’ enabling resources and address this important new barrier for PLWH.

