**Participant Consent:** Once the participant contacts the study team through a study flyer, letter, clinical trials database, or provider referral, the study will be explained with an emphasis on the use of random assignment to study groups. The consent process will be completed in a private area of the Bartlett Specialty Practice. To account for low levels of literacy, the study materials have been developed on a 5th grade reading level. Participants will also be given the option to have the consent form read aloud in its entirety. The consent form will be maintained in the study files and participants will be given the option of taking a copy of the signed consent form with them. They will be informed that retention of the form may lead to a breach of confidentiality if the information is shared with someone who does not already know their HIV and/or HCV status.

**Assessment of Protocol Comprehension Prior to Signing Consent:** After the consent form is read by the participant or aloud, the study team member will evaluate comprehension with three protocol-specific questions: 1) What are the problems we are trying to improve?; 2) How does this study plan to improve these problems?; 3) How will you be assigned to the different options in this study? We will deem the participant to have an acceptable level of comprehension based on his/her ability to answer those questions.

**Allocation:** This RCT will be conducted and reported following the CONSORT clinical trial guidelines. The study design is pictured in Figure 1. After recruitment and informed consent, patients will be randomized to the nurse case management intervention group or to the usual care group electronically. Participants will be randomized in a 1:1 fashion using REDCap, a secure online data collection program, to ensure balanced, random assignment to the intervention and usual care groups. REDCap employs a simple randomization technique. This strategy will ensure that the study team has no a priori knowledge of group assignment when enrolling and randomizing study participants.

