with scores of 20 or greater (severe) will be referred to their primary provider, or, if the primary provider is not available, the covering urgent provider of the day, for further evaluation before the study is continued.

All questions in the protocol will be asked in a private area and can be administered by a study team member in 30-45 minutes. In addition to the subject questionnaire, each instrument contains a section for the research team to interrogate the patient's medical record to verify specific pieces of the medical history. These variables of interest include:

- CD4+ T cell count
- HIV viral load
- Prescribed HIV treatment
- Year of HCV diagnosis
- HCV RNA
- Fibrosis score
- HCV genotype
- HCV referral history
- HCV appointment history
- HCV treatment initiation barriers
- Hopkins appointment no-show rate

In addition to baseline and outcome data collection, monthly activity logs will be collected for each study participant, independent of allocated study arm. The type, quantity, and content of all encounters with a study participant in the Johns Hopkins system will be recorded each month, including nurse visits. This will define usual care for Bartlett Specialty Practice patients. The type, quantity, and content of all Care2Cure study visits will also be recorded to define the dose of the intervention. Data will be collected from the study participant's Epic record and the interventionist's notes.

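### Baseline HIV regimen is collected in both arms and largely determines who needs an ART change and Phase 2 coordination, but neither Aim 2 analysis uses it, so Aim 2 cannot show whether coordination helps those eligible for it

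*Combined protocol and SAP*

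**What the plan says.** Section 7 (Study Statistics, Secondary Outcome) compares days from randomization to HCV treatment between arms. Kaplan-Meier curves are drawn and "a log-rank test will be used to test the difference"; no strata are named. A Cox model follows with ten covariates: age, sex, race/ethnicity and "HCV knowledge, substance use, fibrosis score, CD4+ T cell count, HIV viral load, care giving responsibilities, and participation in Cure Club) will be included". HIV regimen and drug-interaction status are not among them, nor among the same ten in the exploratory logistic model for linkage. No subgroup or interaction analysis by need for an ART change is planned.

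The regimen is nevertheless available. Section 4 (Data Collection Measures) lists "Prescribed HIV treatment" among the variables taken from the medical record, and Study Duration in the same section confirms a baseline record review in both groups.

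The protocol treats this factor as central at the treatment stage. Section 3 (Background) reports that "the prevalence of interactions was as high as 88.4% depending on the HIV and HCV regimens" and that "Modifying HIV treatment regimens can take months and deter PLWH from starting HCV treatment". Section 4 (Phase 2 – Treatment Initiation) gives a usual wait of 3 to 6 months for the next HIV primary care visit, and a viral load recheck 4 to 8 weeks after a change. Phase 2 coordination is triggered only when there is a decision to start HCV treatment and a contraindicated interaction with current ART.

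**The concern.** Follow-up for Aim 2 is six months. By the protocol's own account, a usual-care participant who needs an ART change may spend much of that time waiting, and may be censored for that reason alone. The same factor is also the gate to Phase 2. It is therefore a plausible strong predictor of the outcome and the natural modifier of the Phase 2 effect. Age, CD4+ count and the other listed covariates do not stand in for it.

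Two things are at stake. Leaving out a prognostic baseline factor can cost some power and pull the marginal hazard ratio toward 1. And a single pooled hazard ratio averages participants eligible for coordination with those who are not. If that ratio is near 1, the reader cannot tell whether coordination failed or was averaged with people who were never offered it.

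**Working it through.** **1. The plan's own figure.** Section 7 (Sample Size Justification) states 90% power for a hazard ratio of 2 with 100 participants. For two-sided 0.05 and 90% power, (1.960 + 1.282)² = 10.51.
- Schoenfeld: 4 × 10.51 / (ln 2)² = 42.04 / 0.480, or 88 events. With 100 events, √100 × 0.693 / 2 − 1.960 = 1.506, which is 93.4% power.
- Freedman: 10.51 × [(2 + 1)/(2 − 1)]² = 94.6, or 95 events. With 100 events, √100 / 3 − 1.960 = 1.373, which is 91.5% power.

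So 90% is reproduced only if nearly all 100 start treatment. With 50 events, Schoenfeld power is 68.8%. That is a separate issue, but it means Aim 2 has little information to spare.

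**2. Inputs for the comparison.**
- From the documents: "The significance level will be set at 0.05. All tests will be two-tailed and analyzed by intention-to-treat"; "Participants will be randomized in a 1:1 fashion using REDCap" and "REDCap employs a simple randomization technique"; censoring at six months (182 days); hazard ratio 2; 100 linked participants; linkage 40% v 60%.
- Assumed, because the documents do not give them: the share needing an ART change (the only figure is an upper limit of about 88%); the hazard multiplier for needing a change; six-month initiation in controls not needing one.

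**3. Linked subset, same hazard ratio of 2 in both classes.** N = 100, 70% control initiation, exponential times, 3,000 simulated trials per cell (Monte Carlo standard error at most √(0.25/3000) = 0.9 points). Log-rank power, unstratified → stratified by class:

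| Share needing change | Multiplier 0.25 | Multiplier 0.5 |
|---|---|---|
| 30% | 67.8 → 79.0 (+11.2) | 80.8 → 84.0 (+3.2) |
| 50% | 59.9 → 73.5 (+13.6) | 77.3 → 80.7 (+3.4) |
| 70% | 54.6 → 66.4 (+11.8) | 74.5 → 76.8 (+2.3) |
| 88% | 53.0 → 58.1 (+5.1) | 75.0 → 75.7 (+0.7) |

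At multiplier 0.25 with control initiation of 40%, the gain is about 5 to 6 points at shares of 30–50% and under 2 points at 88%. Misclassifying 15% of participants shrinks the gains further. A multiplier below 0.25 would enlarge them; the documents support no particular value.

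**4. Intention-to-treat.** N = 200, linkage 40% v 60%, non-linkers never treated, 70% initiation, hazard ratio 2 after linkage. At multiplier 0.25: 96.2 → 97.1 (share 30%), 92.7 → 94.9 (50%), 88.2 → 88.8 (88%). At multiplier 0.5 the change is −0.3 to +0.4 points. Other runs (multipliers 0.33 and 0.5; an effect after linkage either absent or confined to those needing a change) gave about −1 to +2 points, for both the stratified log-rank test and the adjusted Cox model.

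**5. Effect only in those needing a change.**
- By formula, with 88 events, half of them in that class, and hazard ratio 2 there: mean log hazard ratio 0.5 × 0.693 = 0.347, a hazard ratio of 1.41. Then √88 × 0.347 / 2 − 1.960 = −0.33, or 37% power. With 88% of events in that class, the averaged hazard ratio is 1.84 and power is 82%.
- By simulation in the linked subset (hazard ratio 2.5 in that class, 1 elsewhere; share 50%; multiplier 0.25; 70% initiation): pooled 25.1%, stratified 21.4%, within class 49.7%. Stratifying does not undo the averaging; the within-class estimate is what shows the effect.
- The same effect pattern under intention-to-treat, with the linkage difference included: pooled 80.0%, within class 75.8%. These levels move with the assumed time to linkage.

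**The case against.** The strongest objection is that the larger gains belong to an analysis set at odds with the plan's own rule. Section 7 says all tests are by intention-to-treat, with time counted from randomization. On that basis the power gain is about zero, and the pooled test is no weaker than the within-class one in step 5. This stands. The Sample Size Justification does describe a linked-only set for this outcome, so the documents leave both readings open. With 40% v 60% linkage, however, that set would not be split 1:1 as simulated.

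Second, Aim 2 tests the whole intervention, and Phase 1 linkage support reaches everyone in the intervention arm. A reader might infer that participants without an interaction cannot benefit. The documents do not support that; they are ineligible only for the ART coordination.

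Third, a reader might infer that baseline ART alone decides who needs a change. It does not. Background makes interaction depend on both regimens, and Phase 2 judges it against the regimen anticipated in the HCV visit note, after randomization. A baseline class is a proxy.

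Fourth, section 7 says baseline differences between groups will be adjusted for, so regimen could enter the model. That clause acts only if the arms happen to differ. It gives no estimate by class, and it does not use a prognostic factor when the arms are balanced.

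Finally, an unstratified log-rank test is standard and valid. That too stands.

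**Conclusion.** The omission is real, and its consequence is limited. It affects efficiency and interpretation and is not an error of validity: leaving regimen out does not bias the randomized comparison.

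A reader might infer that Aim 2 is materially underpowered because of this omission, or that stratifying would rescue a diluted effect. The documents support neither. The gain runs from about zero (intention-to-treat with 40%/60% linkage) to about 14 points (linked subset, share 50%, multiplier 0.25, 70% control initiation). It is at most about 5 points at these multipliers if 88% fall in one class, and nil or slightly negative when only one class benefits. The share, multiplier and initiation rate are all assumptions.

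The loss that does not depend on those values is that no planned analysis separates participants eligible for coordination from the rest, so Aim 2 cannot say whether Phase 2 helps those it is meant for. Even a within-class hazard ratio includes Phase 1. The contrast between classes is the nearest the design comes to isolating Phase 2, and it will be imprecise. This is a cheap, worthwhile addition.

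**What to change.** In section 7, before outcome data are examined by arm:

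1. Define a two-level baseline class: current ART has, or does not have, a contraindicated interaction with a pre-specified set of HCV regimens in use at the clinic. Use a fixed version of the DHHS HIV/HCV drug table that Phase 2 already relies on. Code it from the baseline record for every participant, blind to arm. State how participants with no prescribed ART are coded, since the inclusion criteria do not require ART. Do not use the HCV visit note or the ART change recorded at six months, because both arise after randomization.
2. Add the class to the Cox model as a covariate or a stratum, and say which.
3. Report the arm hazard ratio with confidence interval within each class, and the arm-by-class interaction, labelled exploratory.

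The cost is SAP wording and one coding step on data already abstracted, with no new visits. The downsides are that the class is a proxy because the HCV regimen is chosen after randomization, within-class estimates will be imprecise, and little is gained if nearly everyone falls in one class. Adjustment or stratification alone does not remove dilution when only one class benefits, so step 3 should not be dropped in favour of step 2.
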